8.3.5 Week 12 only

1. Blood for CTC. One CellSave tube (7.5 ml) will be drawn.
2. Disease assessment (CT of chest, abdomen and pelvis for subjects with measurable disease [unless indicated sooner by clinical findings] or Bone Scan for subjects with bone only disease, or PET/CT). PET/CT can be used in place if CT scan is diagnostic.
3. 12-Lead EKG

8.3.6 Every 16 weeks (after week 12)

1. Disease assessment (CT of chest, abdomen and pelvis for subjects with measurable disease [unless indicated sooner by clinical findings] or Bone Scan for subjects with bone only disease, or PET/CT). PET/CT can be used in place if CT scan is diagnostic.
2. 12-Lead EKG

8.4 Follow-Up Assessments

The following assessments will be performed following completion of study treatment.

1. Physical examination including body weight.
2. Vital signs
3. Disease assessment (CT of chest, abdomen and pelvis for subjects with measurable disease; CT/MRI or Bone Scan for subjects with bone only disease, or PET/CT) PET/CT can be used in place if CT scan is diagnostic.
4. ECOG Performance Status.
5. 12-Lead EKG
6. Laboratory assessments including:
 - a. Clinical chemistry laboratory tests: Blood urea nitrogen (BUN), Creatinine, Calcium, Potassium, Sodium, Glucose, and Hematology: Hematocrit (HCT)
 - b. Hematology: Hematocrit (HCT), Hemoglobin (HGB), Platelet count, White blood cell count (WBC), and differential.
7. Blood for CTC at the first visit documenting disease progression if measurable ONLY. One CellSave tube (7.5 ml) will be drawn.
8. Record any AE(s) and SAEs and assign appropriate grade (NCI [CTCAE v4](#)).
9. Record all concomitant medications(s) added and/or changed.

Patients will be followed for four weeks after removal from study or until death, whichever occurs first. Patients removed from study for unacceptable adverse events will be followed until resolution or stabilization of the adverse event.

8.5 Correlative studies:

1. CTC quantification: peripheral blood will be collected for CTC at baseline, at 4 weeks and 12 weeks, then at the first visit documenting disease progression.
2. Evaluate PI3K/AKT and PTEN mutation on archival tissue sample and fresh tissue if available: PI3K/AKT and PTEN mutation will be tested on paraffin-embedded tumor tissue by DNA sequencing, this data will be compared to the mutation study obtain from CTC at the time of study entry and during the treatment.
3. Exploratory analysis of CTC will be undertaken depending on the number of CTCs for:
 - a. Estrogen receptor
 - b. PI3K/AKT and PTEN
 - c. Other genes based on availability of DNA and RNA and depending on the gene panel utilized for this trial
4. Changes in immune signature: serum will be collected within two weeks of study start and at 4 weeks. Immune signature (cytokines and chemokines) including: IL-4, IL-16, IP-10, IL-12, CSF-1, TIMP-1, OPN, HGF, SDF-1a and TRAIL will be measured by ELISA (Appendix IV)

9.0 Criteria for Evaluation

9.1 Response Definitions

Measurable Lesion: Bidimensionally measurable, with clearly defined margins on physical exams, x-ray, or scan. At least one diameter must be greater than 0.5 cm. Bone lesions are not included.

Evaluable Disease: Unidimensionally measurable lesions, masses with margins not clearly defined, palpable nodal disease, lesions with both diameters less than .5 cm, bone disease. Markers which have been shown to be highly correlated with extent of disease are also considered evaluable.

Non-Evaluable Disease: Pleural effusions, ascites, disease documented by indirect evidence only (e.g., by lab values which don't qualify as evaluable).

Objective Status: To be recorded at each evaluation: If an organ has too many measurable lesions to measure at each evaluation, choose three to be followed before the patient is entered on study. The remaining measurable lesions in that organ will be considered evaluable for the purpose of objective status determination. Unless progression is observed, objective status can only be determined when ALL measurable and evaluable sites and lesions are assessed.

Complete Response (CR): Complete disappearance of all measurable and evaluable disease. No new lesions. If patient has effusions, ascites or disease assessable by surgical restaging (e.g., testicular and extragonadal germ cell cancer), disease must be cytology negative. Patients with markers or indirect evidence of involvement must have normalization of abnormal values. All measurable, evaluable and non-evaluable lesions and sites must be assessed.

Partial Response (PR): Applies only to patients with at least one measurable lesion greater than or equal to 50% decrease under baseline in the sum of the products of perpendicular diameters of all measurable lesions. No progression of evaluable disease. No new lesions. All measurable and evaluable lesions and sites must be assessed

Stable: Does not qualify for complete response, partial response or progression. All measurable and evaluable sites and lesions must be assessed.

Progression: 25% increase or an increase of 10 sq. cm (whichever is smaller) in the sum of products of measurable lesions over smallest sum observed (over baseline if no decrease), OR appearance of any lesion which had disappeared, OR clear worsening of any evaluable disease, OR appearance of any new lesion/site, OR failure to return for evaluation due to deteriorating condition (unless deterioration is clearly unrelated to this cancer). For scan only bone disease, increased uptake does not constitute clear worsening and new lesions are required for progression. Worsening of existing non-evaluable disease does not constitute progression.

Best Response: This will be calculated from the serial evaluation of objective status. For patients with all disease sites assessed every three to six weeks, two objective determinations of CR, will be required for a best response of CR; two of PR or better, but not qualifying for CR, will be required for PR; two of stable or better, but not qualifying as PR or CR, will be required for stable; and patients with objective status of progression on or before the second evaluation (second AFTER the prestudy evaluation) will have a best response of increasing disease.

9.2 Toxicity Definitions

All study toxicities will be graded by the NCI Common Terminology Criteria Version 4.0.

10.0 Criteria for Termination

10.1 Conditions for Terminating the Study

The Study Chair may terminate the study for any of the following reasons:

- Significant toxicities
- If it becomes clear that the study treatment is less effective than standard treatment
- Once all data have been completed.

10.2 Conditions for Individual Patient Termination

The Principal Investigator at each site may terminate the participation of an individual patient for any of the following reasons:

- Disease progression
- Need for exclusionary concurrent treatment
- Withdrawal of informed consent
- Protocol non-compliance
- Lost to follow-up.

11.0 Drug Information

11.1 Drug Name

Pazopanib.

11.1.1 Mode of Action

Pazopanib is a novel compound being developed for the treatment of various cancers. Pazopanib is a potent, multi-targeted TKI of VEGFR-1, -2, -3, PDGFR- α and - β and c-kit, with IC₅₀ values of 10, 30, 47, 71, 84 and 74 nM, respectively inhibits VEGF induced VEGFR-2 phosphorylation in human umbilical vein endothelial cells (HUVEC) as well as in mouse lungs in a dose-dependent manner. Pazopanib shows significant growth inhibition of a variety of human tumor xenografts in mice, and also inhibits bFGF- and VEGF-induced angiogenesis in two mouse models of angiogenesis, the Matrigel plug assay and the cornea micropocket model.

11.1.2 Shipment, Storage and Stability

Investigational product must be dispensed or administered according to procedures described herein, and in accordance with procedures at each participating site. Study drugs will be shipped from the drug manufacturer directly to the participating sites for direct distribution of the drugs to the study patients. The participating site will be responsible for drug accountability at their site. Only subjects enrolled in the study may receive investigational product, in accordance with all applicable regulatory requirements. Only the site pharmacist or authorized site personnel may supply or administer investigational product. Investigational product will be dispatched to the site only after receipt of required documents in accordance with applicable regulatory requirements and Novartis Pharmaceuticals procedures.

Investigational product(s) will be dispensed to the subject on Day 1 after it has been confirmed that the subject meets all eligibility criteria and all screening assessments have been completed and the results reviewed. Subjects are to return to the site approximately every 4 weeks for re-supply of investigational product(s).

11.1.4 Incompatibilities

Concomitant Medications and Non-Drug Therapies

If future changes are made to the list of permitted/prohibited medications, formal documentation will be provided by Novartis Pharmaceuticals and stored in the study file. Any such changes will be communicated to the investigative sites in the form of a letter.

Permitted Medications

All subjects will be asked to provide a complete list of prescription and over-the-counter medications that have been taken within the 4 weeks prior to Screening. The investigator must be informed as soon as possible about any new medication(s) taken from the time of Screening until the completion of the post-treatment follow-up visit.

All concomitant medications taken during the study will be recorded in the electronic case report form (eCRF) with indication, dose information, and dates of administration.

Subjects should receive full supportive care during the study, including transfusion of blood and blood products, and treatment with antibiotics, analgesics, erythropoietin, or bisphosphonates, when appropriate.

Anti-emetics (such as prochlorperazine, lorazepam, ondansetron or other 5-HT antagonists) may be administered prophylactically in the event of nausea. Anti-diarrheals, such as loperamide, may be administered as needed in the event of diarrhea. Although acetaminophen at doses of ≤ 2 g/day is permitted, it should be used with caution in subjects with impaired liver function.

Permitted Medications – Use with Caution

Specific recommendations regarding anticoagulants:

Results from drug-drug interaction studies conducted in subjects with cancer suggest that pazopanib has no effect on the metabolism of S-warfarin. Hemorrhagic events, however, have been reported in clinical studies with pazopanib; therefore, pazopanib should be used with caution in subjects with increased risk of severe bleeding or who are receiving concomitant anticoagulant therapy (e.g., warfarin or its derivatives, low molecular weight heparin, unfractionated heparin). Subjects taking concomitant anticoagulant therapy should be monitored regularly for changes in relevant coagulation parameters as clinically indicated, as well as for any clinical bleeding episodes.

Specific recommendations regarding hypoglycemic therapy including insulin:

Results from drug-drug interaction studies conducted in subjects with cancer suggest that there will be no clinically relevant pharmacokinetic interaction between pazopanib and hypoglycemic agents. Transient decreases in serum glucose (mainly Grade 1 and 2, rarely Grade 3) have been observed in clinical studies with pazopanib. In addition, decreases in blood sugar have been recently reported in subjects treated with another small molecule tyrosine kinase inhibitor, sunitinib [51]. Such changes may require an adjustment in the dose of hypoglycemic and/or insulin therapy. Subjects should be advised to report symptoms of hypoglycemia (e.g., confusion, visual disturbances, palpitations, sweating). Serum glucose should be tested during treatment with pazopanib as outlined in the protocol and as clinically indicated.

Effects of Concomitant Pazopanib and Simvastatin

A potential interaction with concomitant administration of 800 mg of pazopanib and simvastatin has been identified in oncology studies. Pooled data from 11 clinical studies in which cancer patients received pazopanib monotherapy revealed that the incidence of ALT elevation >3 X ULN increased with concomitant pazopanib and simvastatin therapy (11/41 patients; 27%) compared with the incidence with pazopanib and no concomitant statin therapy (126/895 patients; 14%). Due to the lower systemic exposures achieved with both eye drops and low-dose oral pazopanib tablets, and the frequency of liver function monitoring, the use of simvastatin or other statins has been permitted during clinical trials.

The Effects of Pazopanib on Other Drugs

In vitro data indicate that pazopanib is a potential inhibitor for CYP3A4, CYP2C8, CYP2D6, CYP1A2, CYP2C9, CYP2C19, CYP2A6, CYP2B6, and CYP2E1. Pregnane

X receptor transient transfection assay suggested some potential for human CYP3A4 induction at high concentrations. Results from drug-drug interaction studies conducted in subjects with cancer suggest that pazopanib is a weak inhibitor of CYP3A4, CYP2C8, and CYP2D6 *in vivo*, but had no clinically relevant effect on CYP1A2, CYP2C9 or CYP2C19 metabolism. Therefore, concomitant use of pazopanib with certain medications (substrates of CYP3A4, CYP2C8, and CYP2D6) with a narrow therapeutic window should be undertaken with **CAUTION** due to the potential for alterations in the pharmacologic effects of these medications or an increased risk for serious or life threatening adverse events associated with such medications (see below) secondary to the inhibition of specific CYP enzymes by pazopanib. In addition, the potential for drug interaction with such medications, although diminished, may persist after the last dose of pazopanib due to its long half-life (i.e., mean 30.9 hours); therefore, continue to exercise **CAUTION** for at least 7 days and up to 15 days after the last dose of pazopanib when administering these medications. These medications include (but are not limited to):

- Ergot derivatives: dihydroergotamine, ergonovine, ergotamine, methylergonovine (potential increased risk for developing ergot toxicity that includes severe vasospasm leading to peripheral as well as cerebral ischemia)
- Neuroleptics: pimozide (potential increased risk for QT interval prolongation, ventricular arrhythmia, and sudden death)
- Antiarrhythmics: bepridil, flecainide, lidocaine, mexiletine, amiodarone, quinidine, propafenone (potential increased risk for QT interval prolongation and Torsade de Pointes)
- Immune modulators: cyclosporine, tacrolimus, sirolimus (potential increased risk for nephrotoxicity and neurotoxicity)
- Miscellaneous: quetiapine, risperidone, clozapine, atomoxetine.

In this trial, treatment with these medications while on study treatment is prohibited.

The Effects of Other Drugs on Pazopanib

Results from *in vitro* studies suggest that the oxidative metabolism of pazopanib in human liver microsomes is mediated primarily by CYP3A4, with minor contributions from CYP1A2 and CYP2C8. Furthermore, *in vitro* data suggest that pazopanib is a substrate for p-glycoprotein. Substances that induce or inhibit CYP3A4 may alter the pharmacologic effects of pazopanib and should be used with **CAUTION**.

Medications that inhibit CYP3A4 may result in increased plasma pazopanib concentrations. Selection of an alternate concomitant medication with no or minimal potential to inhibit CYP3A4 is recommended. A dose reduction to 400 mg pazopanib should be considered when it must be co-administered with strong CYP3A4 inhibitors.

Strong CYP3A4 inhibitors include (but are not limited to):

- Antibiotics: clarithromycin, telithromycin, troleandomycin
- HIV: protease inhibitors (ritonavir, indinavir, saquinavir, nelfinavir, amprenavir, lopinavir)

- Antifungals: itraconzaole, ketoconazole, voriconazole, fluconazole
- Antidepressants: nefazodone
- Diet: grapefruit, seville oranges, starfruit, and their juices

CYP3A4 inducers may decrease plasma pazopanib concentrations. Selection of an alternate concomitant medication with no or minimal enzyme induction potential is recommended.

Drugs that induce CYP3A4 and may decrease pazopanib plasma concentrations include (but are not limited to):

- Glucocorticoids: cortisone (>50 mg), hydrocortisone (>40 mg), prednisone (>10 mg), methylprednisolone (>8 mg), dexamethasone (>1.5 mg)
- Anticonvulsants: phenytoin, carbamezepine, phenobarbital, oxcarbazepine
- HIV antivirals: efavirenz, nevirapine
- Antibiotics: rifampin (rifampicin), rifabutin, rifapentine
- Miscellaneous: St. John's Wort, modafinil, pioglitazone, troglitazone

Prohibited Medications

Subjects should not receive other anti-cancer therapy [cytotoxic, biologic, radiation (other than leuprolide or other GnRH agonists)] while on treatment in this study.

Medications that inhibit CYP3A4 may result in increased plasma pazopanib concentrations; therefore, co-administration of strong CYP3A4 inhibitors is **PROHIBITED** beginning 7 days prior to the first dose of study drug until discontinuation from the study. **Strong CYP3A4 inhibitors include (but are not limited to):**

- Antibiotics: clarithromycin, telithromycin, troleandomycin
- HIV: protease inhibitors (ritonavir, indinavir, saquinavir, nelfinavir, amprenavir, lopinavir)
- Antifungals: itraconzaole, ketoconazole, voriconazole, fluconazole
- Antidepressants: nefazodone
- Diet: grapefruit, seville oranges, starfruit, and their juices at or near time of drug ingestion

11.1.5. Side Effects

See Section 7.0

12.0 Statistical Considerations

The response rate with no additional treatment in women with disease progression while receiving aromatase inhibitors is expected to be <5%. We will consider an overall response rate of 20% to be clinically meaningful. For the purpose of this study, response will be defined as clinical benefit rate, including complete response, partial response, and stable disease for at least 12 weeks.

Therefore, we used the American Cancer Society's website (http://cryptnet.net/kepner/one_sample.html) for a 2 stage design with $p_0=0.05$, $p_1=0.20$ and power 80% at $\alpha=5\%$. This design specifies that if 0 of the first 14 eligible and evaluable subjects do not respond to the treatment at 12 weeks, then we are unlikely to reach a true overall response rate of 20%. The 15th patient will not be enrolled until we have confirmed that we have met criteria of at least 1 responses (response defined as clinical benefit) observed in the first 14 patients, to proceed to the second stage. An additional 13 patients will be enrolled in stage 2 for a total of 27 patients. If at least 4 of the total patients respond, we will conclude that the addition of pazopanib in this setting has the possibility of reversing resistance to hormone therapy with aromatase inhibitors. Using this design, we will have a less than 5% chance of incorrectly accepting the null hypothesis ($\alpha=0.05$), and an 80% chance of correctly rejecting the null hypothesis ($\beta=0.2$).

To determine whether the level of cytokines at baseline and during treatment could predict response to antiangiogenic therapy, we will divide patients into two groups; responder and non-responder group. The student t test will be used to analyze the differences of cytokine levels at baseline and at 4 weeks between these 2 groups.

CTC quantification data will be correlated with response and time to progression.

We will make preliminary observations regarding mutations or deletions in PIK3CA and PTEN in patients with measurable CTC, correlating changes with response and disease history, as well as presence or absence of these alterations in archival tumor tissue.

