The most common adverse reactions (greater than or equal to 20%) were diarrhea, hypertension, hair color changes, nausea, anorexia, and vomiting. Grade 3/4 adverse reactions that differed by greater than or equal to 2% between arms were abnormal hepatic function, diarrhea, hypertension, and proteinuria. QT prolongation has been seen with pazopanib. Laboratory abnormalities occurring in >10% of patients and more commonly (>5%) in the pazopanib arm included increased transaminases, hyperglycemia, leukopenia, hyperbilirubinemia, neutropenia, hypophosphatemia, thrombocytopenia, lymphocytopenia, hyponatremia, hypomagnesemia, and hypoglycemia. Deaths due to serious adverse events include cerebrovascular accident, gastric cancer, gastrointestinal hemorrhage, hemoptysis, bowel perforation, cardiac failure, myocardial infarction, hepatic failure and pneumonia occurred more commonly in the pazopanib arm. Hepatic dysfunction is included as a boxed warning in the product label and two deaths were associated with hepatic failure.

Recently, a phase II trial was designed for patients with metastatic breast cancer, who failed 2-3 prior chemotherapy. Total 20 patients were recruited in this study, 70% were ER+, and all were Her-2/neu negative. Pazopanib monotherapy was given at 800 mg daily. One patient (5%) had a partial response, 11 (55%) had stable disease (SD) [four (20%) with SD > or = 6 months], and seven (35%) had progressive disease as their best response. One (5%) was not evaluable. The median time to progression was 5.3 months. Pazopanib did not cause significant severe toxicity aside from grade 3-4 transaminitis, hypertension, and neutropenia in three patients each (14% each) and grade 3 gastrointestinal hemorrhage in one patient (5%)[18].

Standard therapy for hormone receptor positive metastatic disease.

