12.1 Endpoint Definitions

Primary endpoint:

- The primary endpoint of this study is clinical benefit (including complete response, partial response, and stable disease) of at least 12 weeks.

Secondary endpoint:

- PFS: evaluate progression free survival in patients treated with the combination of pazopanib and a NSAI in this trial
- Safety : adverse events, SAEs

Exploratory endpoints:

- Evaluate the impact of the combination of pazopanib and a NSAI on circulating tumor cells
- Evaluate the change of immune profile with the combination of pazopanib and a NSAI

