12.3 Estimated Duration of Study

Enrollment will occur over 18 months.

Follow-up 6-8 months after last subject enrolled

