12.6 Sample Size

With 30 patients enrolled, we expect 27 for evaluation at 12 weeks. The two-stage design has 80% power to detect clinical benefit (defined as complete or partial response or stable disease) in 20% of patients compared to <5% of patients without this treatment.

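### The <5% null is unsupported for an endpoint that counts stable disease at 12 weeks, so meeting 4 of 27 shows only a rate above 5%, not reversal of resistance

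*Combined protocol and SAP*

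**What the plan says.** Section 12.0 (Statistical Considerations) sets the null: "The response rate with no additional treatment in women with disease progression while receiving aromatase inhibitors is expected to be <5" (per cent). The alternative follows: "We will consider an overall response rate of 20% to be clinically meaningful". The next sentence defines the term for this study: "response will be defined as clinical benefit rate, including complete response, partial response, and stable disease for at least 12 weeks". Section 12.1 repeats the definition as the primary endpoint.

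Section 12.6 (Sample Size) leaves no doubt that the null is meant for clinical benefit. It describes the power to detect clinical benefit "in 20% of patients compared to <5% of patients without this treatment".

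The design has two stages. The trial stops if none of the first 14 patients benefits; otherwise 13 more are enrolled. With at least 4 of 27 benefiting, Section 12.0 concludes that adding pazopanib may reverse resistance to aromatase inhibitors. Section 3.1 describes a single-arm trial, so the null is the only comparator.

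**The concern.** A rate below 5% is easy to accept for tumour shrinkage on a drug that has already failed. It is a much stronger claim when not having progressed by week 12 also counts. Several features of the plan make stability easier to reach than shrinkage:

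- Under Section 9.1, stable disease is the residual category: anything that is not complete response, partial response or progression.
- Progression by size is judged against the smallest sum on study, or against baseline if there was no decrease. Growth that qualified a patient for entry does not count again.
- For disease seen only on bone scan, increased uptake is not progression; new lesions are needed. Section 3.2 admits patients with bone lesions as their evaluable disease.
- Sections 3.1 and 3.2 require documented progression on the aromatase inhibitor but set no minimum pace of disease.

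If the background rate of 12-week stability is well above 5%, the rule can be met by slow disease alone. The stated 5% error rate would then not describe the risk of wrongly concluding that resistance may have been reversed.

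**Working it through.** **1. The plan's own figures.** Inputs from Section 12.0: n1 = 14, continue if X1 ≥ 1; n2 = 13; success if X1 + X2 ≥ 4; p0 = 0.05, p1 = 0.20.

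P(success | p) = Σ over x ≥ 1 of P(X1 = x) × P(X2 ≥ 4 − x), with X1 ~ Bin(14, p), X2 ~ Bin(13, p), and the second factor equal to 1 for x ≥ 4.

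At p = 0.05: 0.3593 × 0.0245 + 0.1229 × 0.1354 + 0.0259 × 0.4867 + 0.0042 = 0.042. At p = 0.20 the same sum gives 0.807. Both agree with the stated 5% and 80%. The arithmetic holds, so the question is the input p0.

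**2. What p0 = 5% requires.** Without any model, at least 95% of patients on the aromatase inhibitor alone must have progressed by week 12 (84 days). Turning this into a median needs a distribution, which the documents do not give.

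- Exponential: median = 84 × ln 2 / ln 20 = 84 × 0.6931 / 2.9957 = 19.4 days. The ±7-day window in Section 8.0 gives 17.8 to 21.1 days.
- Weibull with shape k: median = 84 / (ln 20 / ln 2)^(1/k) = 84 / 4.322^(1/k). Shapes 0.7, 1.5, 2 and 3 give about 10, 32, 40 and 52 days.

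**3. The rule if the combination does nothing.** The background rates below are assumptions. The step needs no survival model.

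| Background 12-week rate | Stage 1 passed, 1 − (1 − p)^14 | 4-of-27 rule met |
|---|---|---|
| 5% | 51% | 4.2% |
| 10% | 77% | 27% |
| 15% | 90% | 58% |
| 20% | 96% | 81% |
| 30% | 99% | 98% |

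At 15%, for example: 0.2539 × 0.3080 + 0.2912 × 0.6017 + 0.2056 × 0.8791 + 0.1465 = 0.581. Solving P(success) = 0.05 gives p of about 5.3%; solving for 0.50 gives about 13.6%.

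**4. Cut-offs that keep alpha at or below 5%** (same 14 + 13 patients and stage 1 rule):

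| p0 | Needed of 27 | Exact alpha | Power at p0 + 15 points |
|---|---|---|---|
| 10% | 6 | 0.047 | 70% |
| 15% | 8 | 0.040 | 59% |
| 20% | 10 | 0.030 | 48% |
| 30% | 13 | 0.036 | 44% |

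**5. What 4 of 27 shows.** The observed rate is 4/27 = 14.8%. The exact (Clopper-Pearson) 95% interval is 4.2% to 33.7%. The exact 90% interval, which corresponds to a one-sided 5% test, is 5.2% to 30.8%.

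**The case against.** The strongest reply is that no one has shown the background rate to be high. Entrants have radiographic progression on the same drug, which favours early further progression, and no section reports a rate for patients who simply continue it. This stands. The success chances above are conditional on assumed rates, and the rule is met more often than not only if the background is about 13.6% or more. A reader might infer that an inactive combination would usually pass; the documents do not establish that.

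A reader might also infer that the null is true only if untreated patients progress with a median of about 19 days. That figure depends on exponential progression. With a rising hazard the median could be 52 days and 5% would still be right. Measuring from a screening scan taken up to 21 days before dosing (Section 8.0) lengthens even the exponential figure to 105 × 0.6931 / 2.9957 = 24 days.

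The protocol's monotherapy study, where "The median time to progression was 5.3 months", might be read as the background. It is not, because those patients were taking pazopanib. The same applies to the 66% stable disease cited in Section 1.3 with bevacizumab added to failing hormone therapy.

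Nor is 5% simply a shrinkage rate left under a changed endpoint, since Section 12.6 assigns it to clinical benefit outright. The fault is missing support.

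It is also fair to say that Section 2.1 only asks to evaluate the clinical benefit rate, which the trial will do; that Section 12.0 words its conclusion cautiously; that Section 1.3 foresees randomized phase II testing next; and that stage 1 is a futility gate, which stops 49% of trials at a true 5%. These points limit the harm. They do not supply a basis for p0, and the conclusion about resistance still rests on it.

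**Conclusion.** The concern holds as a matter of an unsupported null. The stated alpha is correct at a background rate of 5% (exact 0.042) and is lost above about 5.3%, so there is almost no margin for error in a figure with no source. Over assumed background rates of 10% to 30%, the chance that an inactive combination meets the rule runs from 27% to 98%. Which value applies cannot be settled from the documents. Meeting 4 of 27 therefore supports a 12-week clinical benefit rate above 5% and nothing further about resistance.

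A reader might think that moving the 5% test to the next scheduled scan would cure this. Section 8.3.6 puts that scan at week 12 + 16 = 28 (196 days). Under exponential progression, the 4-of-27 rule applied to week-28 status is met by an inactive combination 4.5% of the time at a 1.5-month background median (5.1% progression-free), but 32% at 2 months (10.7%) and 67% at 2.5 months (16.8%). It moves the same unsupported figure to another visit.

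**What to change.** In Section 12.0, with Sections 12.1 and 12.6 aligned:

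1. Replace the conclusion attached to 4 of 27 with a statement that it shows a 12-week clinical benefit rate above 5%, and that without a control arm it does not show reversal of resistance.
2. Report the observed rate with an exact confidence interval, and state its level. A 90% interval matches the one-sided 5% test; at exactly 4 of 27 a 95% interval would include 5% and appear to contradict a positive result.
3. Tabulate the rule's false-positive chance for background rates from 5% to 30%.
4. Either give evidence that fewer than 5% of patients continuing the aromatase inhibitor alone are free of progression at week 12, or adopt a higher p0 with its cut-off at n = 27 (6, 8, 10 or 13 for 10%, 15%, 20% or 30%) and restate the power (70%, 59%, 48% or 44% for a 15-point gain).

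Clinical benefit at week 28 can be added as a supportive result, but not as the primary test with the same 5% null. It would report after the final analysis set in Section 12.5 (12 weeks after last enrolment). Week 28 is 196 / 30.44 = 6.4 months, just beyond the lower end of Section 12.3: "Follow-up 6-8 months after last subject enrolled". It would also need a rule for patients who leave early, because Section 8.4 generally follows them for only four weeks.

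The core changes are to wording and reporting, with no added patients, visits or scans. The price is a weaker permitted conclusion or, with a higher p0, lower stated power.
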